Study Intervention Description	
The following will be offered to all female youth (N=1200):
 
 (1) HIV Testing Services (HTS) via home-based or community based recruitment strategies (2) HIV testing approaches that females can choose from include: (a) oral fluid HIV self-testing (OraQuick ADVANCE® Rapid HIV-1/2 Antibody Test, OraSure Technologies) at their convenience; (b) staff-aided testing at home/mobile site; and (c) a referral to a health care facility where HIV testing will be done by a health care provider (standard facility-based HTS) (3) Behavioral survey at baseline visit (4) SMS HIV test experience satisfaction survey (5) Staff-administered questionnaire about self-testing for females who choose self-testing option. 
For all HIV positive females:
 
All HIV positive females will receive the following;
 
 (1) Point of care (POC) CD4 cell count at baseline (2) Viral load testing using dried blood spot (DBS) at 0 and 12 months (3) Referral for care and treatment; Adaptive linkage to care intervention. All HIV positive participants (N≈108) will be randomized to receive standard referral (N≈54) or standard referral plus SMS message (N≈54) to link to HIV care and treatment services; those who do not link to care within 2 weeks will be re-randomized in a ratio of 1:1 to a second SMS message or a one-time economic incentive to link to care.

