Primary Endpoint(s)	
Primary outcomes of interest for Aim 1 are based on the HIV prevention and treatment continua as outlined below:
 
 • Recruitment/Seek: Ability to identify and recruit female youth that are high risk for HIV infection using two seek strategies (home-based vs. community-based) 
 ○ The proportion of youth in the community who accept study screening (estimated from total youth approached as the denominator); ○ The proportion of youth who accept study enrollment (estimated from youth screened and eligible as the denominator); • Testing: 
 ○ Testing uptake by different testing modalities; ○ Completion of confirmatory testing; ○ Proportion that are positive; ○ Among those who are positive, completion of baseline collection of CD4 and viral load tests. 
Outcomes of interest for Aim 3 economic evaluation to determine the comparative cost effectiveness of the seek, test, link, and prevention interventions are:
 
 • Compute the cost per HIV-infected female youth identified under each 'seek' strategy (home-based vs. community based); • Compute the cost per HIV-infected female youth identified under each 'test' strategy (self-testing, staff delivered HTS testing, standard facility-based HTS); • Calculate the incremental cost-effectiveness ratio of the adaptive linkage to care intervention among HIV positive female youth; • Compute the cost of the SMS prevention intervention among HIV negative female youth.
Secondary Endpoint(s)	
Secondary outcomes of interest for Aim 2 are based on the HIV prevention and treatment continua as outlined below:
 
 • Linkage to Care: 
 ○ Percent of females who tested positive that attended a first HIV care appointment at an HIV Comprehensive Care Center (CCC) ○ Time to link to care after positive confirmatory test result. • Retention in Care: 
 ○ Completion of viral load testing at 12 months; ○ Reported appointment attendance via SMS and verification by study staff at 3, 6, 9, and 12 months. • Primary Prevention (N≈185): 
 ○ Proportion reporting HIV risk behaviors, and condom use, at 6 and 12 months; ○ Proportion who re-tested at 12 months; ○ Proportion who tested positive at 12 months.

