8. STUDY OBJECTIVES

Primary Objectives

- (1) To determine the preferred recruitment venue and testing modality that targets and finds the highest number of HIV infected and at risk female youth aged 15-24 years in Homa Bay County, Nyanza region, western Kenya. This will be determined by examining uptake and yield of previously undiagnosed HIV infection of the two 'seek' strategies (community or home-based) and the three 'test' strategies (self-testing, HTS in a mobile/home setting, or facility-based HTS) among female youth;
- (2) To conduct an economic evaluation, using cost effectiveness analyses to determine the relative utility of each seek, test, link, and prevention intervention.

Secondary Objectives

- (1) To pilot and evaluate an adaptive intervention to link newly diagnosed HIV-positive female youth to treatment and care services;
- (2) To identify barriers and facilitators to seeking HIV care services after receiving a positive diagnosis;
- (3) To identify barriers and facilitators to seeking HIV prevention services for high risk female youth after receiving a negative HIV test result;
- (4) To provide an HIV prevention intervention to a randomly selected subset of high-risk negatives (motivational text message with referral for combination prevention interventions), and to re-test them at 12 months.

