Adaptive Intervention Pilot: Descriptive statistics and survival plots will be used to characterize occurrence and timing of linkage among girls responding to the initial SMS message and girls in each augmented treatment condition. Survival analysis (Singer & Willett, 2003; Therneau & Grambsch, 2000) will determine which approach to augmenting linkage – continued SMS or economic incentives – is more effective in linking female youth newly diagnosed with HIV to care sooner. Using the Cox Proportional Hazards Model, difference in the likelihood and timing of linkage between treatment conditions will be quantified with an interval estimate of the hazard ratio. Median time to linkage also will be estimated and compared across treatment conditions.

Cost Effective Analysis

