Linkage to Care: Percent of females who tested positive that attended a first HIV care appointment at a CCC; time to link to care after positive confirmatory result.	GIRLS study project database, medical record review at CCC, exit interviews.	2 weeks after first randomization; 1 week to re-randomize; 2 weeks after second randomization (5 weeks total from start of linkage pilot). Exit interview collected at 12 months.	Descriptive statistics; survival plots for occurrence and timing of linkage. Cox proportional hazards model for differences in likelihood and timing of linkage between the two treatment conditions; median time to linkage. Predictors of successful linkage to care.	N≈108
Retention in Care: Completion of viral load testing one year after positive confirmatory test; self-report of appointment attendance. Review of medical records to confirm self-report of clinic attendance.	SMS surveys, medical record review, exit interviews.	3, 6, 9, 12 months for SMS surveys. Medical record review to confirm clinic attendance self-report. Exit interview collected at 12 months.	Frequencies; assess number retained in care at 12 months. Proportion who complete viral load testing at 12 months.	N≈108
Primary Prevention: HIV risk behaviors, condom use, and HIV re-testing of a sub-sample of high risk HIV negatives	SMS surveys GIRLS study project database	6 and 12 months for SMS surveys. At 12 months, exit interview and re-testing	Descriptive statistics; new HIV diagnosis at 12 months.	N≈185
Aim 3 economic evaluation	Measures (Sources)	Data Collection Timeline	Data Analysis	
Economic evaluation to determine the comparative cost effectiveness of the seek, test, link, and prevention interventions.	GIRLS study project database	Accrual and follow-up period.	Micro-costing of the cost per HIV infected person under each seek and test strategy; incremental cost effectiveness of linkage to care intervention for HIV +; cost analysis of SMS intervention and re-testing for HIV negative females.	

15.10 Appropriate Methods and Timing for Analyzing Outcome Measures.

See Table 1: Evaluation Plan.

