With this estimate of the expected percentage of girls with newly diagnosed HIV infection, we asked how small of an increase in the odds of newly diagnosed HIV infection could be detected with 80% power when community-based recruitment is compared to home-based recruitment. With 600 youth recruited by each strategy, power is 80% to detect an odds ratio of 1.67, in other words, a modest increase from 9% to 14% newly diagnosed with HIV infection. When comparing testing approaches, and assuming an equal proportion of girls prefers each approach and testing approach does not interact with recruitment strategy, power is 80% to detect an odds ratio of 1.85. If there is an interaction between recruitment strategy and testing approach, when comparing

testing approaches within a recruitment strategy (i.e., estimating simple main effects), power is 80% to detect an odds ratio of 2.32.

These calculations show the proposed sample size (N=1200) is capable of detecting modest differences in the yield of newly diagnosed HIV infection across both recruitment strategies and testing approaches.

Among the approximately 108 female youth we expect to be newly diagnosed with HIV infection, about 20% are expected to successfully initiate HIV care at a health facility after a single SMS message. The remaining 80% (N=86) who are not linked to care after the initial SMS message will be randomly assigned to either continued SMS messages or to economic incentives. Assuming at least 60% are linked to care at some point during follow-up, survival analysis employing Cox regression will be able to detect a hazard ratio of 2.2 describing the impact of treatment condition (continued SMS vs. economic incentives) on the occurrence and timing of successful linkage to care at a health facility, with 80% power.

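### The linkage pilot randomises girls at two stages, but no planned analysis compares the first-stage arms or estimates linkage under the four embedded strategies

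*Combined protocol and SAP*

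**What the plan says.** Aim 2a (section 8) is "To pilot and evaluate an adaptive intervention to link newly diagnosed HIV-positive female youth to treatment and care services". Its linkage endpoint in the Protocol Summary is "Percent of females who tested positive that attended a first HIV care appointment at an HIV Comprehensive Care Center (CCC"), together with time to link after the confirmatory positive result. Both refer to every girl who tests positive.

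The design has two randomisations. In the Protocol Summary, all HIV-positive girls "will be randomized to receive standard referral (N≈54) or standard referral plus SMS message (N≈54"). At the second stage, "those who do not link to care within 2 weeks will be re-randomized in a ratio of 1:1 to a second SMS message"; the other option there is an incentive paid once. Sections 11.6.1 and 15.12 describe the same scheme. Two options at each stage give four embedded strategies.

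The analysis in section 13.2 (Adaptive Intervention Pilot) has two parts. Descriptive statistics and survival plots show "occurrence and timing of linkage among girls responding to the initial SMS message and girls in each augmented treatment condition". Survival analysis with a Cox model then determines "which approach to augmenting linkage – continued SMS or economic incentives – is more effective". The Linkage row of Table 1 describes the Cox model as addressing "differences in likelihood and timing of linkage between the two treatment conditions". Section 15.11 sizes that comparison on the girls left after early linkers are removed: "The remaining 80% (N=86) who are not linked to care after the initial SMS message will be randomly assigned".

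**The concern.** The analysis does not use the first randomisation. About 54 girls are allocated to each first-stage arm, yet no section states a comparison of those arms or an estimate of linkage under any complete strategy.

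The plotted groups do not fill the gap. Responding to the initial SMS means having linked, so that curve reaches 100% by definition. Girls who start on referral alone and link without further help appear in none of the named groups. Sections 13.2 and 15.11 are worded as if all 108 girls receive the initial SMS, whereas the design gives it to about half.

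At stake is whether the pilot can report its own endpoint, for all positives, by what the girls were randomised to. The incremental cost-effectiveness ratio of the adaptive intervention (Aim 3, section 13.2) also needs a linkage effect for the intervention as a whole. The text refers only to effectiveness results, without naming the estimate or the comparator.

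**Working it through.** **1. Which girls the Cox model covers.** Inputs from section 15.11: 108 positives, 20% linked after the first stage, at least 60% of the rest linked, hazard ratio 2.2, 80% power. Alpha is not stated; two-sided 0.05 is assumed.

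- Girls not linked: 0.80 × 108 = 86.4, given as 86.
- Expected events: 0.60 × 86 = 51.6.
- Events required (Schoenfeld, 1:1): 4 × (1.960 + 0.842)² / (ln 2.2)² = 31.4 / 0.622 = 50.5, so 51.
- Power with 51.6 events is 80.8%; the detectable hazard ratio is 2.18.

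The plan's 2.2 reproduces from the 86 girls. The Cox comparison is therefore the second-stage contrast, without the roughly 22 early linkers (0.20 × 108 = 21.6).

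**2. What it leaves undetermined.** Linkage under a strategy is r + (1 − r)p, where r is first-stage linkage in the assigned arm and p is linkage among the re-randomised under the assigned second option. The documents give no r for each arm. For illustration, take hazard ratio 2.2 with a mean of 60% linked among the re-randomised. Solving (S + S^2.2)/2 = 0.40 gives S = 0.541, so p is 45.9% with second SMS and 74.1% with incentive. Now vary r between arms, keeping its average at 20%, so that the 86 girls and the Cox result stay the same:

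| r: referral / referral+SMS | Referral, then SMS | Referral, then incentive | SMS, then SMS | SMS, then incentive |
|---|---|---|---|---|
| 20% / 20% | 56.7% | 79.3% | 56.7% | 79.3% |
| 15% / 25% | 54.0% | 78.0% | 59.4% | 80.6% |
| 10% / 30% | 51.3% | 76.7% | 62.1% | 81.9% |
| 5% / 35% | 48.6% | 75.4% | 64.8% | 83.2% |

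The second-stage hazard ratio is 2.2 in every row, while the first-stage difference runs from 0 to 30 points. The Cox model cannot tell these rows apart.

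**3. Girls with no plotted group.** At 5% to 20% linkage after referral alone, 54 × 0.05 = 2.7 to 54 × 0.20 = 10.8, so about 3 to 11 girls.

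**4. Precision of the missing estimates.** With 54 girls per first-stage arm and non-linkers split 1:1, the variance is (1 − p)² r(1 − r)/54 + (1 − r) p(1 − p)/27.

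- At r = 20%, p = 45.9%: 0.00087 + 0.00736 = 0.00822, a 95% half-width of 17.8 points.
- At r = 20%, p = 74.1%: half-width 15.0 points. Across the table the range is about 14 to 19 points.
- Referral then SMS against SMS then incentive, first row: difference 22.6 points, standard error 11.9, power about 48%; the difference detectable with 80% power is about 33 points.
- By first-stage arm, 20% + 80% × 60% = 68% linked, half-width 1.96 × √(0.68 × 0.32/54) = 12.4 points. At two weeks, 54 per arm give about 80% power for 20% against 45%.

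**The case against.** The strongest reply is that the plan answers the question it asks. Section 11.6.1 sets out to compare SMS and incentive in girls who need augmented linkage support, sections 9.1 and 13.1 speak of two enhancements, and no section promises to rank four strategies. The plots are descriptive, and timing among responders is a fair thing to describe. Section 13.2 (Other Analysis) also plans a logistic regression of timely linkage among newly diagnosed girls, with interactions by treatment condition. The Linkage row of Table 1 gives N≈108, and its two treatment conditions are not defined. This is also a secondary pilot aim with about 108 girls.

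Much of this stands. The second-stage question is legitimate, and the Cox model answers it. It would be wrong to say that the plan has no other model involving treatment condition. But the logistic model is exploratory, is built around baseline predictors and their interactions, and does not yield linkage by strategy. If Table 1 means the first-stage arms, it conflicts with sections 13.2 and 15.11; if it means the second stage, the first is not analysed. Neither reading covers the four strategies. Small numbers argue for intervals, not for omitting the estimates.

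A reader might also infer three stronger faults that the documents do not support:

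- **The Cox comparison is biased because it leaves out early linkers.** Those girls were never randomised between SMS and incentive. Starting at re-randomisation is right for that contrast.
- **The second-stage effect is overstated by 25%.** The ratio of 28.2 points among non-linkers to 22.6 among all girls is 1/0.80. It is a change of denominator, under an assumed 20% early linkage in both arms, and no section presents one figure as the other.
- **The second-stage cost-effectiveness ratio is inflated.** After the same first stage, extra cost and extra linkage both arise only in non-linkers. Spread over all girls, both are multiplied by 0.80 and the ratio is unchanged. Distortion would need mixed denominators, which the plan does not propose.

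**Conclusion.** The point holds as a gap between design and analysis. The first randomisation has no stated comparison, the four strategies have no stated estimate, and the descriptive grouping is conditioned on the outcome and omits girls who link after referral alone. Aim 2a's endpoint is therefore not delivered by arm or strategy. The randomised second-stage result is unaffected.

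The size is the information forgone. In the illustration, one second-stage result is compatible with 48.6% to 56.7% linked under referral then SMS, and with 79.3% to 83.2% under SMS then incentive. These figures rest on assumed first-stage rates by arm, on a detectable (not expected) hazard ratio, and on a 60% rate that section 15.11 states for some point during follow-up, not for five weeks. They show what is undetermined and forecast nothing. The change should be made, but it concerns a secondary pilot aim.

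**What to change.** In section 13.2 (Adaptive Intervention Pilot) and the Linkage row of Table 1:

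- Replace the responder grouping with time-to-linkage curves from the confirmatory test, and percent linked at the end of the five-week schedule, by randomised first-stage arm and by each of the four embedded strategies, using all randomised girls.
- For the strategy estimates, use inverse-probability weights: 2 for girls linked before re-randomisation (1 ÷ ½) and 4 for re-randomised girls (1 ÷ (½ × ½)), with robust intervals, because an early linker counts towards both strategies that begin with her arm. The first-stage arm comparison needs no weights.
- Keep the Cox model, labelled as the effect of incentive against second SMS among girls not linked at re-randomisation, and define the two treatment conditions in Table 1 accordingly.
- State that any cost-effectiveness ratio for the whole adaptive intervention uses the strategy-level percentages, with costs and effects on the same denominator.

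The cost is revised wording and a short weighted analysis of data already being collected, with no extra girls or procedures. The drawback is imprecision: roughly ±15 to 18 points per strategy under the assumed equal first-stage rates. The text should present these results as estimates with intervals, not as tests.

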Primary Objectives	
(1) To determine the preferred recruitment venue and testing modality that targets and finds the highest number of HIV infected and at risk female youth aged 15-24 years in Homa Bay County, Nyanza region, western Kenya (Aim 1).
 
 • This will be determined by examining the uptake and yield of previously undiagnosed HIV infection of the two (2) 'seek' strategies (community or home-based) and the three (3) 'test' strategies (self-testing, HTS in a home/mobile setting, or facility-based HTS) among female youth; 
(2) To conduct an economic evaluation, using cost effectiveness analyses to determine the relative utility of each seek, test, link, and prevention intervention (Aim 3).

Secondary Objective	
(1) To pilot and evaluate an adaptive intervention to link newly diagnosed HIV-positive female youth to treatment and care services (Aim 2a);
 
(2) To identify barriers and facilitators to seeking HIV care services after receiving a positive diagnosis (Aim 2b);
 
(3) To identify barriers and facilitators to seeking HIV prevention services for high risk female youth after receiving a negative HIV test result (Aim 2c);

	(4) To provide an HIV prevention intervention to a randomly selected subset of high risk negatives (N≈185) (motivational text message, with referral for combination prevention interventions), and to re-test them at 12 months (Aim 2d).

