The sample size for the linkage to care adaptive intervention pilot is an estimate of the number of female youth with previously undiagnosed HIV infection we anticipate reaching. The expected percentage of girls testing positive was based on our MP3 Youth pilot study (data not yet published), and we expect 9% of all tested girls to have HIV infection not previously diagnosed. Thus given a total sample size of 1,200 female youth, we anticipate enrolling about 108 previously undiagnosed HIV positive females in the adaptive intervention pilot to link HIV positive female youth to HIV treatment and care.

Sampling method: We will stratify the sample by conveniently selected sub-counties; Homa Bay municipality, Mbita sub-county and Ndhiwa sub-county. Mapping of catchment areas surrounding health facilities will be used to establish relationships with referral clinics. We select a random starting point that is within walking distance (about 5km) of the catchment area of the health facility. Approximately four hundred (400) participants will be recruited from each stratum and for each stratum it is assumed that 200 participants will be recruited through each recruitment approach. Both recruitment strategies (household and mobile event) will run concurrently until the desired sample size is reached. If needed for sample size attainment, we will expand the sampling area to a 6 - 10 km circumference of the referral clinic.

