In order to determine costs, we will conduct a micro-costing of the cost per HIV-infected person identified under each ‘seek’ and ‘test’ strategy. This will be followed by an incremental cost-effectiveness analysis of the linkage to care interventions among HIV-infected, and a cost analysis of the SMS intervention among HIV-uninfected, women. These costs will include all costs required to deliver each intervention (home visits, staff time, supplies, and monitoring). Data will primarily utilize a micro-costing methodology that uses project expenditure and management records, employing structured costing spreadsheets that record each resource, category (e.g., personnel, supplies), quantity (e.g., hours), and unit costs. The cost data for the self-test group will include costs of obtaining a confirmatory test for those with positive self-testing results. The cost data will be stratified by HIV testing venue (home based, community based (mobile), or referral facility). With these cost data, we will calculate and compare the cost per HIV-infected person identified in each HTC strategy. We will also evaluate the costs of the linkage interventions per individual successfully linked to care. The results of the economic evaluation will allow us to identify the most efficient, affordable way to seek high risk young women and test them. For the linkage interventions, we will utilize the cost data as well as the effectiveness results to compute the ICER for the novel linkage intervention that is used. The ICER will reveal whether the costs of achieving the incremental gains from additional linkage intervention(s) suggest whether it is cost-effective or not. These results will provide novel data on the cost-effectiveness of linkage to care interventions for high-risk females in sub-Saharan Africa.

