15.11 Sample Size Considerations

Baseline sample size calculation

Based on our experience with MP3 Youth (data not yet published), which screened N=788 female youth and enrolled N=690 female youth over a period of eight months (November 19, 2014 – June 12, 2015), we expect we can recruit N=1200 female youth over a period of around twice that time. We expect the sample accrual rate to be slower than in MP3 Youth, because we will be recruiting only female youth and mainly those out of school (a large proportion of younger MP3 Youth girls were in school and easier to recruit). In addition, we have two different recruitment strategies, and the home-based strategy may be more labor intensive and time consuming than a community mobile event. We therefore expect a somewhat lower accrual rate. Therefore, in order to stay within the estimate 12 months of recruitment, we will increase our field staff during the implementation phase of the project. Sample size estimates are also based on IRDO's program data and the estimated number of youth in Homa Bay. We expect large numbers of youth will be successfully recruited from the home and mobile events (IRDO reaches tens of thousands of youth/year) for a total sample size of ≥ 1200 female youth.

Power Analysis

Power calculations for Aim 1 are based on the yield of newly diagnosed HIV across recruitment strategies and testing options offered to female youth. Using version 12 of the PASS program (Hintze, 2013) for logistic regression, we did not approach this power analysis from the perspective of calculating a sample size needed to detect a particular effect size with at least 80% power. Rather, because this part of the study (Aim 1) is not a clinical trial but rather an exploration of preferences and yield of recruitment and participant-selected testing strategies, we started with the large, feasible sample size and determined the size of effects that could be detected with at least 80% power when comparing recruitment strategies and HIV testing approaches.

The expected percentage of girls testing positive is based on our MP3 Youth pilot study. In that study, 55 of 636 female youth not previously diagnosed were found to have HIV infection (data not yet published). Thus, we expect about 9% of all tested females in this study to have HIV infection not previously diagnosed.

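### Aim 3 plans to name the most efficient strategy and judge linkage cost-effective or not, but carries no uncertainty into the cost ratios and sets no value for judging the ICER

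*Combined protocol and SAP*

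**What the plan says.** Sections 6, 8 and 13.1 list the economic evaluation as the second primary objective. Section 6 places its outcomes under the primary endpoints: a cost per HIV-infected girl identified for each seek and each test strategy, a cost for the prevention SMS, and, for linkage, "Calculate the incremental cost-effectiveness ratio of the adaptive linkage to care intervention among HIV positive female youth".

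The Cost Effective Analysis part of section 13.2 draws two conclusions from these quantities. For seek and test, the results will "allow us to identify the most efficient, affordable way to seek high risk young women and test them". For linkage, "The ICER will reveal whether the costs of achieving the incremental gains from additional linkage intervention(s) suggest whether it is cost-effective or not".

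Section 13.2 does plan uncertainty for the underlying outcomes. Yield by venue and test approach goes into a logistic regression, and the linkage comparison gets an interval for the Cox hazard ratio. For the cost ratios and the ICER, neither section 13.2 nor Table 1 mentions an interval, resampling, sensitivity analysis, acceptability curve or threshold. Costs come mainly from project expenditure and management records.

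**The concern.** A cost per case is a total cost divided by a count of new diagnoses, and the counts here are small. An ICER divides by a difference in linkage that may be close to zero. Ratios of this kind vary a good deal by chance, and the interval for a hazard ratio or an odds ratio does not show by how much.

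The linkage verdict has a second gap that does not depend on sample size. A cost per extra girl linked cannot show cost-effectiveness until it is set against a value for that outcome, and none is stated.

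Sections 7.1 and 7.3 say the results are meant to inform scale-up policy in Kenya. A strategy named most efficient on a ranking that chance could have produced, or a linkage verdict with no stated criterion, would be a weak basis for that.

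**Working it through.** **Inputs from the plan**
- Yield: "we expect about 9% of all tested females in this study to have HIV infection not previously diagnosed" (section 15.11), based on a pilot in which "55 of 636 female youth not previously diagnosed were found to have HIV infection"; 55/636 = 8.65%, rounded up.
- Cases: "given a total sample size of 1,200 female youth, we anticipate enrolling about 108 previously undiagnosed HIV positive females" (section 10.2); 0.09 × 1200 = 108.
- Venues: 600 girls each, so 0.09 × 600 = 54 cases each.
- Test approaches: equal preference (section 15.11's assumption) gives 1200/3 = 400 girls and 36 cases each.
- Linkage: 86 girls re-randomized 1:1, so 43 per arm; 60% linked; hazard ratio 2.2 (section 15.11).

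**Reproducing the plan's own figures** (two-sided 5%, not stated in the plan but consistent with its results)
- Section 15.11: "With 600 youth recruited by each strategy, power is 80% to detect an odds ratio of 1.67". An odds ratio of 1.67 on 9% gives 14.2%; with 600 per group, power is 80.0%.
- Hazard ratio 2.2 at 80% power needs 51 events (Schoenfeld); 0.6 × 86 = 51.6 are expected.

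The inputs are therefore read as the plan intends.

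**Seek and test: chance difference in cost per case**

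Take two strategies with equal true yield and equal, fixed total cost. The ratio of their costs per case is then the inverse ratio of two binomial counts, with SE(log ratio) = √[2(1/k − 1/n)].

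| Comparison | k, n | SE | Median fold, exp(0.6745 SE) | 95% limit, exp(1.96 SE) |
|---|---|---|---|---|
| Venue | 54, 600 | 0.184 | 1.13 | 1.43 |
| Test | 36, 400 | 0.225 | 1.16 | 1.55 |

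Simulation gives medians of 1.13 and 1.17 and 95% limits of 1.44 and 1.57. For the highest against the lowest of three equally good test approaches, the simulated 95th percentile is 1.72.

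Girls choose their own test, so uptake may be uneven. As an illustration, shares of 10% and 45% give 10.8 and 48.6 cases: SE = √(1/10.8 − 1/120 + 1/48.6 − 1/540) = 0.321, and a limit of 1.88-fold.

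**Chance of reversing a true cost difference** (assumed true ratios, equal yield), Φ(−ln ratio / SE)

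| True cost ratio | Venue | Test |
|---|---|---|
| 0.85 (15% cheaper) | 19% | 23% |
| 1.5-fold | 1.4% | 3.6% |
| 2-fold | 0.01% | 0.1% |

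**Linkage: the ICER denominator** (incentive against second SMS, 43 per arm, proportional hazards, 60% linked on average)
- Hazard ratio 2.2: solving [(1 − S) + (1 − S^2.2)]/2 = 0.6 gives 45.9% and 74.1% linked. Difference 28.2 points; SE = √[(0.459 × 0.541 + 0.741 × 0.259)/43] = 10.1 points; 95% range 8.4 to 48.0. With incremental cost held fixed, the ICER limits differ by 48.0/8.4 = 5.7-fold.
- Hazard ratio 1.5 (an assumed smaller effect): 52.6% and 67.4%; difference 14.8 points, SE 10.4, range −5.7 to 35.2. The range includes zero, so the interval for the ICER is unbounded.

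**The case against.** **The plan is silent on uncertainty; it does not rule it out.** A reader might infer that the plan commits to point ratios alone. It never says so. Yield and linkage carry their own planned inference, and the ICER is to use the effectiveness results. This stands, and it narrows the point: the missing step is carrying that uncertainty into the cost ratios. It does not remove the point, because a conclusion under a primary objective needs its method in the plan.

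**Section 13.2 also plans a societal cost-benefit analysis.** That sets costs against monetised gains, but it does not state a value per extra girl linked, so the criterion for the ICER is still missing.

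**The chance differences are limits, and true differences may be large.** A reader might infer that the ranking will probably be wrong. The figures do not support that: the median chance difference is 1.13 to 1.17-fold, and a true 1.5-fold difference would seldom be reversed. The documents give no full unit costs by strategy, and section 10.2 expects that home recruitment may be more labour intensive. This stands as a limit on size. Only intervals would show which case applies.

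**The case counts do not belong to the linkage ICER.** It is tempting to apply 36 to 54 cases per strategy to the ICER sentence as well. Those counts concern seek and test only. The ICER contrast is itself not fixed: it could be incentive against second SMS, or the first-stage comparison of about 54 against 54. For that reason, and because full delivery costs are not given, no ICER in money is offered here.

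**Resampling girls with their costs does not fully fit the data.** Expenditure records yield largely strategy-level costs, and recruitment runs through households and events. This stands and shapes the remedy.

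**Conclusion.** The point holds in this form: Aim 3 promises an efficiency ranking and a cost-effectiveness verdict, but section 13.2 does not carry the uncertainty in yield, linkage and costs into the ratios, and it gives no value by which to judge the ICER.

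- **Seek and test:** chance alone can separate two equal strategies by up to about 1.43-fold (venue) or 1.55-fold (test) at the 95% limit. This assumes 9% yield, equal and fixed total costs, equal test preference and independent girls. Uneven test choice widens it. Modest true differences could be misranked; large ones rarely.
- **Linkage:** if the contrast is incentive against second SMS, the denominator alone leaves the ICER uncertain about 5.7-fold at the planned effect, and unbounded at an assumed hazard ratio of 1.5.

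The absence of a method is read from the protocol text; the separate study procedures manual was not available. The change should be made before analysis, but it does not call the design into question.

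**What to change.** In the Cost Effective Analysis part of section 13.2:

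1. Replace the sentence saying that the ICER will settle cost-effectiveness.
2. Report each cost per case, and each comparison between strategies, with a 95% interval. Obtain it by resampling outcomes, together with girl-level costs where these are recorded, and respect clustering by household or event.
3. Add sensitivity analysis on shared and unit costs, which resampling girls cannot cover. Intervals will not correct for girls choosing their own test, so say so when test approaches are compared.
4. For linkage, name the contrast. Report incremental cost and incremental linkage, each with an interval, and an acceptability curve over a stated range of values per extra girl linked.
5. Limit any statement that a strategy is most efficient, or that linkage is cost-effective, to what those results support.

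The cost is plan wording, a modest amount of extra analysis and more cautious conclusions. No added participants or study procedures are needed.
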